**Project Title:**

Impact of a Culturally Appropriate Patient Navigator (Promotora Navigator) on Trust and Communication in the Screening Mammography Setting

**Brief Overview/Objectives:**

1. To assess the relationship between level of trust in the healthcare system and active engagement in a mammography screening program in the local Hispanic population.
2. To assess the relationship between health literacy and active engagement in a mammography screening program in the local Hispanic population.
3. To determine whether a Promotora Navigator improves Hispanic women's measures of trust in the healthcare system and provider compared to those receiving standard of care treatment in the screening mammography setting.
4. To determine whether a Promotora Navigator improves Hispanic women's measures of satisfaction with communication when compared to those receiving standard of care treatment in the screening mammography setting.

**Project Plan:****Background:**

Although there has been interval improvement in reducing disparity in mammography utilization in medically underserved communities since the 1990s, significant disparities persist and should be addressed. Culturally adapted patient-targeted healthcare interventions can help reduce ethnic inequalities in access to cancer screening programs. "Promotoras", culturally appropriate patient navigators have been shown to increase screening mammography rates in the Hispanic population. However, there is little evidence on the impact of a Promotora Navigator (PN) program on patient trust in the healthcare system and satisfaction with communication in this setting. This proposal aims to assess the impact of a PN on women's trust in the healthcare system and satisfaction with communication when compared to those receiving standard of care.

The study design is the final outcome of a Partnership Development Grant (PDG) awarded by the Meharry-Vanderbilt Community Engaged Research Core (CERC) to [name] of Vanderbilt University Medical Center and the Mid-South Division of the American Cancer Society. This PDG provided an opportunity to engage numerous community stakeholders in collaboration. The parent study was designed by both academic and community partners and then presented to a community engagement studio for refinement. The final design outcome was submitted for and successfully awarded a CERC Community Engaged Research Grant. Matthew Walker Comprehensive Health Center (MWCHC) will serve as a primary community partner moving forward, providing clinic facilities. MWCHC is an ideal community partner given the center's proven record of providing healthcare services and health education to the local community, regardless of economic status.

As proposed, community partners benefit from education and potential development of a sustainable model for caring for women in developing minority groups. The community will benefit from an increase in well woman screening provided to the local Hispanic population (including those in the control arm). Academic partners will benefit from patient-centered outcomes data on the impact of the PN in the screening mammography setting.

Research Questions/Hypotheses:

Do trust in the healthcare system and/or health literacy impact engagement in a screening mammography program in the local Hispanic population? *We hypothesize that higher levels of trust and health literacy are positively related to engagement in a screening mammography program.*

Does a PN improve Hispanic women’s measures of trust in the healthcare system and satisfaction with communication in the screening mammography setting when compared to those receiving standard of care? *We hypothesize that women with access to a PN will have higher levels of trust in the healthcare system and satisfaction with communication than women receiving the standard of care.*

Methods:

*Study Design:* The study design is a randomized control trial. In this pilot study, 100 participants will be randomized to either a) the intervention, in which they receive care from the PN or b) the control, in which they receive the standard of care.

*PN Identification and Education:*

A PN will be identified and trained by [name], VICC Community Health Educator. [name] will supplement educational materials.

*Inclusion/Exclusion Criteria:*

Inclusion criteria will be Hispanic women meeting United States Preventive Services (USPSTF) criteria for screening mammography and criteria for clinical service coverage through the TN Breast and Cervical Cancer Screening Program.

**Inclusion Criteria:**

- Women
- Identifying as Hispanic ethnicity
- Age 40-64 if no previous mammogram in last two years

**\*\*If uninsured or limited health insurance coverage, TN Breast and Cervical Cancer Screening Program will pay for mammogram**

- Annual household income of less than \$41,150 for a family of 2 persons
- Reside in Tennessee

**Exclusion Criteria:**

- Personal history of breast cancer
- Current breast symptoms (palpable mass)

*Recruitment:*

We aim to recruit 100 women total. All participants will be informed that well woman screening is free under the TN Breast and Cervical Cancer Screening Program. Participants will be offered \$40 gift cards for compensation for participation. Two recruitment methods will be used.:

[figure not shown]
1. The research team will identify and recruit women meeting inclusion criteria from the MWCHC electronic medical record. Eligible participants identified from the MWCHC will be contacted via telephone. **[See recruitment material]**.
2. The research team will identify and recruit women from the local Hispanic community through churches, community organizations, and community events. We will also use radio announcements and Facebook for recruitment **[See recruitment material]**.

At the time of recruitment, women will be assisted in scheduling an appointment at MWCHC for well woman screening during a “Hispanic Clinic Day”.

*Hispanic Clinic Days:*

Women will be scheduled during one of five dedicated “Hispanic Clinic Days”. Each clinic day will host up to 20 women, to a target 100 participants. Each day there will be a morning session for 10 women and an afternoon session for 10 women. The bilingual research assistant and bilingual PN will be present during the Hispanic Clinic Days. At the start of each session, consent will be obtained from all potential participants, followed by baseline assessments, randomization and clinical care. Gift cards will be distributed at time of written consent.

**HISPANIC CLINIC DAY FLOW CHART**

*Consent:*

Written informed consent will be obtained for all participants by the research assistant in person at MWCHC [**see attached consent**].

*Baseline Assessment:*

Immediately following consent, all participants will complete a baseline assessment (English or Spanish according to participant preference) to collect demographic information, trust in healthcare system assessment, and health literacy assessment [**see baseline survey**]. This assessment will be collected by paper and pencil with the help of the research assistant.

*Randomization:*

Women will be randomized to the control arm, the intervention arm 1 (individual education), or the intervention arm 2 (group education) immediately following consent. Randomization will be performed using the random number generator software available in the R statistical package ([www.r-project.org](http://www.r-project.org)).

*Control Arm:*

Immediately following consent and completion of the baseline assessment, women in the control arm will receive standard of care well woman screening. The control arm will receive screening results per MWCHC protocol.

*Intervention Arm 1:*

Immediately following consent and completion of the baseline assessment, women in the intervention arm 1 will participate in a 20-30 minute educational session [**see educational slides**] alone with the PN. Well woman screening will follow the educational session. The PN will be available to assist with questions and language interpretation as necessary. After standard delivery of screening results, the PN will contact these participants to answer any questions about their screening results and to assist with scheduling any additional tests necessary.

*Intervention Arm 2:*

Immediately following consent and completion of the baseline assessment, women in the intervention arm will participate in a 20-30 minute group educational session [**see educational slides**] from the PN. Well woman screening will follow the educational session. The PN will be available to assist with questions and language interpretation as necessary. After standard delivery of screening results, the PN will contact these participants to answer any questions about their screening results and to assist with scheduling any additional tests necessary.

*Post Assessment 2-5 Days After Delivery of Results:*

All participants will be contacted via telephone by the bilingual research assistant 2 -5 days after results are distributed by standard method for post assessment. This will be conducted in English or Spanish according to participant preference. This post assessment will repeat the measures of trust. It will also assess measures of satisfaction with care, satisfaction with communication, relationship with the promotora and intent to follow-up [**see attached post assessment**]. After the post

assessment, the existing Vanderbilt Ingram Cancer Center (VICC) Breast and Cervical Cancer pamphlet [**see attached VICC Breast and Cervical Cancer pamphlet**].

*Delayed Chart Review:*

The bilingual research assistant will perform delayed chart review 2-4 weeks following delivery of results to assess whether patients needing follow-up diagnostic studies returned. Delayed chart review may also occur in 2-3 years to assess adherence to continued screening.

*Data Collection:*

Baseline assessment data will be collected by paper and pencil (in Spanish or English language per patient request) immediately following consent at MWCHC. The bilingual research assistant will be available to assist as necessary. Post assessment data will be collected electronically in REDCap by bilingual research assistant via telephone. Return for Follow-Up data will be accessed via patient medical record. Data will be stored in a REDCap.

*Item Development:*

**Baseline Assessment:** The baseline assessment will collect demographic information. Additionally, the baseline assessment will assess trust in the healthcare system using the Healthcare System Distrust Scale and health literacy using the Self-Reported Health Literacy Scale.

**Post Assessment:** Measures of healthcare system distrust will be repeated in the post assessment. The post assessment will include multiple items to assess satisfaction with care using the Patient Satisfaction with Cancer Scale, satisfaction with communication adapted from the Interpersonal Processes of Care Survey, and satisfaction with the promotora. The post assessment will also assess intent to follow up.

*Statistical Considerations:*

Descriptive statistics will be used to analyze the demographic characteristics of participants. Comparison of knowledge in baseline and post assessments will be assessed with  $\chi^2$ , Student *t* tests and Fischer exact tests as necessary. Open-ended responses will be analyzed qualitatively. Post assessment comparison between “intervention” and “control” groups will be assessed with  $\chi^2$ , Student *t* tests and Fischer exact tests as necessary. Open-ended responses will be analyzed qualitatively.

*Sample Size:*

For this pilot study, the proposed sample size of 50 patients/group provides at least 80% power to detect a 29% improvement of the success rate, i.e. 40% vs 69%, with 2 sided Type 1 error = 5%. This calculation was based on the Chi squared test with the normal approximation correction for continuity.

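### The plan sizes and analyses two groups of 50 but randomises to three arms, with no stated allocation ratio or pooling rule in the readable text

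*Combined protocol and SAP*

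**What the plan says.** Two parts of the protocol describe two groups. Methods, Study Design: "100 participants will be randomized to either a) the intervention, in which they receive care from the PN or b) the control". Sample Size: "the proposed sample size of 50 patients/group provides at least 80% power to detect a 29% improvement of the success rate", for 40% v 69% at a two-sided 5% level. On the method it adds: "This calculation was based on the Chi squared test with the normal approximation correction for continuity". The analysis in Statistical Considerations is also two-group: "Post assessment comparison between “intervention” and “control” groups will be assessed with" the usual two-sample tests.

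The Randomization paragraph describes three: "Women will be randomized to the control arm, the intervention arm 1 (individual education), or the intervention arm 2 (group education) immediately following consent". It names R's random number generator as the tool and gives no ratio. Separate paragraphs follow for the control arm, Intervention Arm 1 and Intervention Arm 2. The Arm 2 paragraph still speaks of a single arm: "women in the intervention arm will participate in a 20-30 minute group educational session".

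The aims point to one contrast, navigator against no navigator. The hypothesis is that "women with access to a PN will have higher levels of trust in the healthcare system and satisfaction with communication than women receiving" standard care. Objective 3 likewise concerns "measures of trust in the healthcare system and provider compared to those receiving standard of care treatment". No objective compares individual with group education.

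**The concern.** Three arms can serve a two-group comparison only if the plan says how three become two: how many women go to each arm, and whether the navigator arms are analysed together. The readable text says neither.

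The gap matters because the allocation list is coded from the Randomization paragraph. A programmer with only that paragraph has to choose a ratio. Equal thirds is a natural choice for three listed arms, while 50/25/25 is the split that matches 50 per group with equal formats. Both are consistent with the paragraph, and only the second keeps the stated power. A written pooling rule would also stop the navigator contrast from being chosen after the data are seen.

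**Working it through.** **Inputs.** From Sample Size: control rate p1 = 0.40, navigator rate p2 = 0.69, two-sided 5% (z = 1.96), chi-squared test with continuity correction, 50 per group. From Study Design: 100 women in total. The allocations other than 50 v 50 are assumptions.

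**Formula (normal approximation).** With n1 controls and n2 navigator women:

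- pooled rate p = (n1·p1 + n2·p2)/(n1 + n2)
- SE0 = √[p(1 − p)(1/n1 + 1/n2)]
- SE1 = √[p1(1 − p1)/n1 + p2(1 − p2)/n2]
- correction c = 0.5(1/n1 + 1/n2)
- power = Φ[(p2 − p1 − c − 1.96·SE0)/SE1]

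The exact figure sums the binomial probabilities of every pair of outcomes for which the same corrected test rejects.

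**The plan's own figure, 50 v 50.** p = 0.545; SE0 = 0.0996; SE1 = 0.0953; c = 0.020. The argument is (0.29 − 0.020 − 1.96 × 0.0996)/0.0953 = 0.785, so power is 78.4%. Exact enumeration gives 80.0%. The corrected sample-size formula asks for 52 per group, close to the stated 50. The plan's figure is therefore reproduced, exactly at the margin by enumeration and slightly short by the approximation.

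**Equal thirds with the navigator arms pooled, 33 v 67.** p = 0.594; SE0 = 0.1044; SE1 = 0.1023; c = 0.0226. The argument is (0.29 − 0.0226 − 1.96 × 0.1044)/0.1023 = 0.613, so power is 73.0%. Exact enumeration gives 74.2%.

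| Control v pooled navigator | Approximation | Exact |
|---|---|---|
| 50 v 50 | 78.4% | 80.0% |
| 48 v 52 | 78.3% | 81.1% |
| 40 v 60 | 76.7% | 76.8% |
| 34 v 66 | 73.7% | 73.5% |
| 33 v 67 | 73.0% | 74.2% |

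**Loss from 50 v 50.** At 33 v 67 it is 78.4 − 73.0 = 5.4 points (approximation) or 80.0 − 74.2 = 5.8 points (exact). At 34 v 66 it is 4.7 or 6.5 points. Exact power moves unevenly with small changes in n, so the first decimal should not be pressed.

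**Detectable navigator rate at 80% power, control 40%.** Going from 50 v 50 to 33 v 67, it rises from 69.5% to 71.2% (approximation) or from 69.0% to 70.9% (exact), about 2 points.

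**Without the continuity correction**, 33 v 67 and 34 v 66 give 79% to 81%, but the plan says the correction was used.

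**The case against.** The strongest reply is that this is under-specification and not contradiction. Study Design defines the intervention as care from the navigator, and both navigator arms fit that definition: each has an education session, help at screening and a call after results. Two formats nested within one navigator group would agree with the hypothesis, the objectives and the planned analysis. The 50 per group out of 100 then points to half the women in control, and at that split no power is lost. The flow chart could not be read and may show the arm sizes. Equal thirds appears nowhere in the text. The trial is a pilot, the success rate in the power statement is not tied to a named endpoint, and the primary outcome under Anticipated Outcomes relates trust to engagement and does not compare arms.

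Most of this stands, and it limits the severity. Pooling is the likeliest intention, and it cannot be claimed that the plan contains no ratio anywhere. The conflict remains, however. The one paragraph that defines allocation lists three arms, the study design and the sample size count two, and no readable sentence joins them. A ratio in the flow chart would still leave the pooling rule unstated in the text. Objectives 3 and 4 and the secondary outcome are arm comparisons, and the only sample-size justification in the plan is a two-group one.

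**Conclusion.** The concern holds as an inconsistency that should be fixed, of low to moderate severity. The wording conflict is certain and the arithmetic is firm. The stated 50 per group and its power describe the trial only if about half the women are controls and the two navigator arms are pooled. If the list were coded as equal thirds, an assumption, power for the pooled comparison would be about 73–74%, and the detectable navigator rate would be about 2 points higher. These figures take the plan's 40% and 69% and its continuity-corrected test as given, with all 100 women analysed. No conclusion is drawn about what the unread flow chart contains.

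**What to change.** Make the three sections agree.

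- **Randomization:** state that women are allocated from a fixed list of 100, with 50 to control, 25 to individual education and 25 to group education, and that the two navigator arms are combined for the comparison with control.
- **Study Design:** state that the intervention is delivered in two formats.
- **Sample Size:** state that the comparison is 50 control v 50 navigator, both formats combined.

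If equal thirds is intended or already in use, keep it, state it together with the pooling rule, and restate the power as about 73–74% for 67 navigator v 33 control.

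**Cost.** Three sentences and a small change to the allocation code, with no extra women. The drawback is 25 rather than about 33 women per format, so a full session of 10 would average 2.5 rather than 3.3 women in group education. With a list shuffled freely over all 100 places, the hypergeometric chance that a full session has 0 or 1 woman in the group arm is about 23%, against about 10% with 33 of 100.

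**Optional mitigation.** Shuffling within each session (5 control, then 2 and 3 or 3 and 2 for the two formats) gives 10/5/5 per clinic day and 50/25/25 over five days. This works as described only when sessions are full. Since Hispanic Clinic Days sets 20 women a day as a maximum, the code would also need a rule for short sessions.

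### The research assistant who works on the clinic days also collects every post-randomization subjective outcome by telephone, in the same interview as the promotora items, and the protocol describes no masking of this interviewer

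*Combined protocol and SAP*

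**What the plan says.** The research assistant's role runs through the whole study.

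- **Consent** (Consent section): "Written informed consent will be obtained for all participants by the research assistant in person at MWCHC".
- **Baseline** (Baseline Assessment): "This assessment will be collected by paper and pencil with the help of the research assistant".
- **Clinic day** (Hispanic Clinic Days): "The bilingual research assistant and bilingual PN will be present during the Hispanic Clinic Days". Sessions hold 10 women, and in each one "consent will be obtained from all potential participants, followed by baseline assessments, randomization and clinical care".
- **Outcome interview** (Post Assessment 2-5 Days After Delivery of Results): "All participants will be contacted via telephone by the bilingual research assistant". Besides repeating trust, the interview covers satisfaction with care, satisfaction with communication, "relationship with the promotora and intent to follow-up".
- **Recording** (Data Collection): "Post assessment data will be collected electronically in REDCap by bilingual research assistant via telephone".

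The arms differ in ways that people on site can see. Control women go straight to screening, arm 1 women have a session alone with the Promotora Navigator (PN), and arm 2 women have a group session with the PN. In both navigator arms the PN also contacts the women after their results.

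The Timeline lists a single research assistant, and no separate assessor appears anywhere. The protocol does not say whether the interviewer is masked, who holds the allocation list, or whether the call follows a fixed script.

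**The concern.** Trust and satisfaction are opinions, given here orally to an interviewer who types in the answers. If the interviewer knows the arm, tone, prompting and the coding of hesitant answers can differ between arms. A woman may also soften criticism when speaking to someone she links with the programme. Only the part of this that differs by arm biases the comparison, but no objective measure of these outcomes exists against which to detect it.

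The comparisons at stake are the randomized ones: objective 3 (trust), objective 4 (satisfaction with communication) and the secondary outcome (satisfaction with communication). The second hypothesis under Research Questions/Hypotheses predicts that the navigator does better. An interviewer who shares that expectation would most plausibly lean the same way. A larger sample would not remove such a bias.

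**Working it through.** **Step 1. Can the interviewer know the arm?** Setting the sections side by side gives three routes.

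1. The assistant is on site for sessions of 10 women in which randomization takes place and some women then go to the PN alone, some in a group and some not at all.
2. Nothing keeps the allocation from the assistant, who also enters the outcome data in REDCap.
3. The interview includes the relationship with the promotora. Women in the navigator arms have also been contacted by the PN after their results, so the arm can surface during the call.

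None of these proves that the assistant knows each woman's arm. Together they make it likely.

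**Step 2. Which outcomes are exposed?** Every subjective outcome measured after randomization comes from this call. Baseline distrust and health literacy do not: they are collected on paper, with the assistant's help. The primary outcome under Anticipated Outcomes relates trust to engagement and does not compare arms.

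**Step 3. The plan's own sample size.** Inputs from the Sample Size section are 40% vs 69%, two-sided 5%, 80% power, and chi-squared with continuity correction.

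- Mean rate: (0.40 + 0.69)/2 = 0.545; difference d = 0.29.
- Uncorrected: n = [1.96·√(2·0.545·0.455) + 0.842·√(0.40·0.60 + 0.69·0.31)]² / 0.29² = (1.380 + 0.567)²/0.0841 ≈ 45.1, so 46 per group.
- Corrected: (45.1/4)·[1 + √(1 + 4/(45.1·0.29))]² ≈ 51.8, so 52 per group.
- Exact power of the corrected test at 50 per group: 0.800.

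The stated 50 per group is reproduced closely, and this point does not dispute it.

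**Step 4. How sensitive is the comparison to interviewer bias?** This is an illustration. Assume no true effect, a true success rate of 40% in both groups, 50 per group, and a bias that adds b to the recorded rate in the navigator group. The documents do not give b.

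The rejection probability is the sum of Bin(x; 50, 0.40)·Bin(y; 50, 0.40 + b) over all pairs (x, y) with

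z = max(|y − x|/50 − 0.02, 0) / √[p̄(1 − p̄)·2/50] > 1.96,

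where p̄ = (x + y)/100 and 0.02 = ½(1/50 + 1/50) is the continuity correction. The uncorrected test omits the 0.02.

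| Assumed b | Corrected | Uncorrected |
|---|---|---|
| 0 | 3.2% | 5.2% |
| 5 points | 5.6% | 8.5% |
| 10 points | 13.4% | 18.4% |
| 15 points | 27.3% | 34.5% |
| 20 points | 46.2% | 54.3% |

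Hand check at b = 10 points by the normal approximation: (0.10 − 0.02 − 1.96·√(0.45·0.55·0.04)) / √(0.24/50 + 0.25/50) = (0.08 − 0.195)/0.099 ≈ −1.16, which gives about 12%, close to the exact 13.4%.

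The Randomization section describes three arms, so the split may not be 50/50. With an assumed 33 controls against 67 women in the pooled navigator arms, the corrected figures are about 3%, 4.9% and 11.5% for b = 0, 5 and 10 points. The pattern is the same.

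**The case against.** The case on the other side has several parts.

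- **Knowledge of the arm is not stated.** No section says that the assistant sees the allocation, runs the randomization or attends the PN sessions. The protocol names a role and does not state that one individual both consents and telephones each woman. This stands: knowledge of the arm is an inference, though a strong one given the small sessions and the single assistant in the Timeline.
- **Item order may already be right.** A reader might infer that promotora items can come before the trust and communication items. The documents do not support that. The order is set by the attached post-assessment form, which is not in the material reviewed, and both lists in the protocol (Post Assessment and Item Development) put the promotora after trust, care and communication. What remains is that the protocol does not fix the order or lock the earlier answers.
- **The direction of bias is not established.** The same role deals with women in all arms, so general politeness towards the interviewer is shared. A reader might infer that the bias must favour the navigator. The stated hypothesis makes that the likelier direction and no more.
- **The magnitude rests on assumed inputs.** The bias is assumed, and the calculation needs a binary success that the protocol never defines for its multi-item scales; Statistical Considerations also allows t tests. This stands, and the table shows sensitivity only.
- **Proportion.** This is a pilot of 100 women who cannot themselves be blinded, so their own reporting bias remains whatever the interviewer knows. This stands too, but the interviewer's contribution is separate and can be reduced without new staff.

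**Conclusion.** The point holds in a limited form. One role recruits, assists and then collects all post-randomization opinions, and no masking is described. The randomized comparisons of trust and of satisfaction with communication are therefore open to interviewer bias.

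The size of that bias cannot be estimated from the documents. An assumed 5 to 10 points on a 40% rate would take the corrected false-positive rate from 3.2% to between 5.6% and 13.4%. That range depends on the assumed bias, a binary success measure and 50 per group.

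Two stronger readings should be resisted. A reader might take 13.4% as this trial's error rate, but it is the result of one assumption. A reader might also conclude that the primary outcome is compromised, but that outcome does not compare arms, and trust is measured at baseline before any contact with the navigator. This is a cheap improvement to the design, not a fault that invalidates it.

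**What to change.** With existing staff:

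1. **Allocation.** A study team member who is neither the assistant nor the PN prepares opaque, sequentially numbered allocations, opened only after the baseline form is complete. Giving them to the PN would put allocation concealment in the hands of the person who delivers the intervention. Keep the arm off the assistant's call sheet and REDCap view.
2. **Interview.** In REDCap, ask the distrust, care and communication items first from a fixed bilingual script, then save and lock them. Next, have the assistant record whether the arm is known or guessed. Only then open the promotora items, on a last page. The order matters, because a question about knowledge of the arm is uninformative once those items have been discussed.
3. **Reporting.** State in the protocol that the interviewer is only partly masked, and report this as a limitation of the arm comparisons.

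The cost is minor form changes and a little of another team member's time. The downside is that masking stays partial, because the assistant is on site and participants cannot be blinded.

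### Distrust is taken on paper in the clinic and later by telephone, so a baseline-to-post change cannot be read as a change in trust; the between-arm comparison is unaffected by a mode shift common to all arms

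*Combined protocol and SAP*

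**What the plan says.** Under Item Development, the baseline instrument for trust is named: "the baseline assessment will assess trust in the healthcare system using the Healthcare System Distrust Scale". The same section says of the later assessment: "Measures of healthcare system distrust will be repeated in the post assessment". No other scale is listed at both times. Health literacy appears only at baseline; satisfaction with care, communication and the promotora appears only afterwards.

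The two measurements are taken differently.

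- **Baseline.** Data Collection says: "Baseline assessment data will be collected by paper and pencil (in Spanish or English language per patient request) immediately following consent at MWCHC". On assistance there are two descriptions. The Baseline Assessment section says "This assessment will be collected by paper and pencil with the help of the research assistant", and Data Collection says "The bilingual research assistant will be available to assist as necessary". Neither says whether items are read aloud or who receives help.
- **Post assessment.** "All participants will be contacted via telephone by the bilingual research assistant 2 -5 days after results are distributed by standard method for post assessment". Data Collection confirms the mode: "Post assessment data will be collected electronically in REDCap by bilingual research assistant via telephone".

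Statistical Considerations then plans two sets of tests. One begins "Comparison of knowledge in baseline and post assessments will be assessed with" and lists chi-squared, t and Fisher tests. The other compares intervention and control at the post assessment. Nothing there mentions the change of mode, and the t test is not described as paired or unpaired.

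**The concern.** A woman may answer questions about her distrust of the healthcare system differently when filling in a form in the clinic and when speaking to study staff by telephone. If so, the two scores would differ even where her trust had not changed. A within-group comparison has no control for this and would count the difference as a change in trust. Mode is not the only thing that changes. The second measurement is also taken away from the clinic, days after results were distributed, and after the screening itself.

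What is at stake is how a fall in distrust within the navigator arms would be reported. Objective 3 concerns the navigator's effect on trust relative to standard of care. A significant within-arm fall could be offered as evidence for that effect when the measurement procedure alone might have produced it.

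**Working it through.** **1. Does the planned comparison concern distrust?** Statistical Considerations says knowledge. The text lists no knowledge instrument at either time, and distrust is the only scale listed at both. Either the sentence has no data behind it or it means distrust. This is an inference: the survey forms are attachments that are not reproduced in the document.

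**2. The plan's own figure.** The document gives no standard deviation, baseline-to-post correlation or mode effect for distrust. Its one calculation is 50 per group for 40% against 69%, two-sided 5%, continuity-corrected chi-squared. It reproduces within two women (52 per group with the correction, 46 without) and does not bear on this point. Only the 50 is carried forward.

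**3. Assumptions.** True change in trust is zero. The procedure shifts the score by m = 0.1, 0.2 or 0.3 SD. SD is 1 at both times. The correlation between the two scores is r = 0.5 or 0.7. The test is two-sided at 5%, with the normal approximation, so only the size of the shift matters and not its direction.

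**4. Paired test, n = 50.** The standard error of the mean change is SE = √(2(1 − r)/n).

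- r = 0.5: SE = √(1/50) = 0.141
- r = 0.7: SE = √(0.6/50) = 0.110

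Rejection probability = 1 − Φ(1.96 − m/SE) + Φ(−1.96 − m/SE).

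| m (SD) | r = 0.5 | r = 0.7 |
|---|---|---|
| 0 | 5% | 5% |
| 0.1 | 11% | 15% |
| 0.2 | 29% | 45% |
| 0.3 | 56% | 78% |

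Example: m = 0.2, r = 0.5 gives m/SE = 1.414, so 1 − Φ(0.546) + Φ(−3.374) = 0.29.

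**5. Unpaired test on the same data, n = 50.** The test wrongly uses SE = √(2/50) = 0.2, so it rejects when the mean change exceeds 1.96 × 0.2 = 0.392 in size. The true SE is still that of step 4. Rejection probability = 1 − Φ((0.392 − m)/SE) + Φ((−0.392 − m)/SE).

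| m (SD) | r = 0.5 | r = 0.7 |
|---|---|---|
| 0.1 | 2% | 0.4% |
| 0.2 | 9% | 4% |
| 0.3 | 26% | 20% |

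These rates are low because the unpaired test ignores the correlation. The estimated change is still off by m whichever test is used.

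**6. Other group sizes, paired test.** Study Design and Sample Size describe two groups, but Randomization describes three arms, so 50 per navigator arm is not assured. With 33 women the rates are 9% to 12%, 21% to 32% and 41% to 60% for the three shifts. With all 100 women pooled they are 17% to 25%, 52% to 73% and 85% to 97%.

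**7. Between-arm comparison.** If every arm is shifted by the same m, the expected difference is (μ + m) − (μ + m) = 0 when the navigator has no effect. A simulation with 50 per arm, r = 0.6 and 20,000 runs agrees. For shifts of 0.1, 0.2 and 0.3 SD the between-arm test rejected in 4.9%, 4.8% and 4.7% of runs, while the paired within-arm test rejected in 12%, 34% and 65%.

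**The case against.** The strongest reply is that the randomised question is untouched. Objective 3 and the stated hypothesis are comparative, a separate post-assessment comparison of intervention and control is planned, and every arm has the same mode at each time. This stands. A reader might infer that the change of mode biases the estimated navigator effect. That would require the shift to differ by arm, for instance if contact with the navigator changed how candidly women answer an interviewer. The documents neither show nor exclude this.

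A second reply is that the contrast is softer than paper against interview suggests, because the research assistant helps with the paper form. This also stands, to an unknown degree.

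A reader might go further and infer that help goes to women who read with difficulty, so that baseline mode follows health literacy and distorts Objectives 1 and 2. The documents do not say who is helped or how, so this is conjecture. The later telephone call cannot affect a baseline exposure. Adjusting the literacy analysis for assistance could also remove real literacy effect if help does follow literacy.

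A third reply is that every rejection rate rests on assumed inputs and that the high ones need a paired test. That is correct, and it is why both tests are shown.

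What none of these replies answers is that a baseline-to-post test is planned with no control comparison and no caveat.

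**Conclusion.** The point holds for the within-group baseline-to-post comparison only. As planned, that comparison cannot tell a change in trust from a change of mode, setting, timing and receipt of results. That it concerns distrust at all is the best reading of the text, since distrust is the only scale listed twice, but the sentence itself says knowledge.

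The size cannot be taken from the documents. Under the assumed shifts of 0.1 to 0.3 SD and correlations of 0.5 to 0.7, with 50 women and no true change, a paired test would be significant in about 11% to 78% of trials and an unpaired test in about 0.4% to 26%. Neither the existence nor the direction of a mode effect is established by the documents. The randomised comparison keeps its nominal error rate if the shift is common to all arms. The matter is therefore modest for Objective 3 as a randomised question, and material for any conclusion about trust drawn from within-arm change.

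**What to change.** In Statistical Considerations:

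1. Replace knowledge with the distrust score, if that is what is meant.
2. State that a navigator effect on trust is concluded only from the between-arm difference in post-assessment distrust, preferably adjusted for baseline distrust.
3. State that within-arm baseline-to-post change is reported descriptively, without a test.

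Optionally, add one field to the baseline form recording whether it was assisted or self-completed. Use it only in a sensitivity analysis of the trust and engagement relationship, and not as a routine adjustment of the literacy analysis.

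The cost is a few words of text, the loss of a significance test on within-arm change, and possibly one form field. Using the same mode at both times, by reading the items aloud privately to every woman at baseline, would remove the mode difference. It is a trade-off rather than a simple gain: sessions hold 10 women, and the plan refers to one research assistant, who also obtains consent. It would also leave the changes in setting, timing and receipt of results in place.
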